### **6.2.3. Additional Analyses of the Primary Endpoint**

The statistical methods for the main analysis will be repeated using the PP population. The analysis will also be performed using the observed data without imputation for missing in both the PP population and the ITT population.

### **6.2.4. Secondary Efficacy Endpoints**

The secondary efficacy endpoints include:

- Percent change from baseline in the ALODEX score at Week 24 (Visit 9), also described as mean percent regrowth,
- Mean change from baseline in SALT score at Week 24 (Visit 9)
- Mean change from baseline in ALODEX score at Week 24 (Visit 9)
- Proportion of subjects in each treatment arm achieving  $\geq 50\%$  hair regrowth compared with baseline using a separate model for SALT and for ALODEX scores
- Change from baseline in the Scalp-AAP-PRO and Scalp-AT/AU-PRO at Week 24 (Visit 9)
- Change from baseline in the Scalp-AAP-ClinRO and Scalp-AT/AU-PRO at Week 24 (Visit 9)
- Change from baseline in the PhGIS-AAP and PhGIS-AT/AU at Week 24 (Visit 9)
- Change from baseline in AFHA-ClinRO at Week 24
- Change from baseline in AFHA-PRO at Week 24
- Change from baseline in the SGIS-AAP and SGIS-AT/AU at Week 24 (Visit 9)
- Change from baseline in SGSHQ-AAP and SGSHQ-AT/AU at Week 24
- Change from baseline in the subject reported AIA at Week 24 (Visit 9)

- SGITS-AAP and SGITS-AT/AU at Week 24 (Visit 9)
- Change in DLQI total score between Baseline and Week 24 (Visit 9)
- PhGIC at Week 24 (Visit 9)
- SGIC at Week 24 (Visit 9)

#### **6.2.5. Secondary Efficacy Analysis**

Descriptive statistics will be presented for all secondary efficacy endpoints.

The mean percent change from baseline in the ALODEX score (percent regrowth); the mean change from baseline in SALT and the mean change from baseline in ALODEX will be analyzed using the methods planned for the primary efficacy analysis. The calculated DLQI total score ranges from 0 to 30. This mean change from baseline in DLQI will also utilize the MMRM analysis as planned for the primary efficacy analysis.

Responder-type analyses are planned based on the SALT, ALODEX, Scalp-ClinRO, and Scalp-PRO. The responder definitions include:

- The proportion of subjects achieving a  $\geq 50\%$  hair regrowth compared with baseline for SALT and for ALODEX scores
- Proportion of subjects achieving an absolute SALT score  $\leq 10$
- Proportion of subjects with  $\geq 2$ -point improvement in Scalp-ClinRO for the Target Area (patchy AA subjects only)
- Proportion of subjects with  $\geq 2$ -point improvement in Scalp-PRO for the Target Area (patchy AA subjects only)
- Proportion of subjects with  $\geq 1$ -point improvement in Scalp-ClinRO for the entire scalp
- Proportion of subjects with  $\geq 1$ -point improvement in Scalp-PRO for the entire scalp

The observed proportion of responders and associated 95% CI will be presented. Adjusted rates and 95% CI will be obtained from a logistic regression model with a factor for treatment. The p-value for the overall global test that  $\beta=0$  for this factor will be presented. The adjusted odds ratios (95% CI) for being a responder (active/placebo oral suspension) will be presented along with the associated p-value.

The questionnaires Scalp-PRO, Scalp-ClinRO, PhGIS, AFHA, and SGIS are collected on a 1-5 scale. The SGRHQ questionnaire is collected on a 1-7 scale. The frequency of responses for each value will be reported by visit and treatment group. Additionally, change status will be categorized as “Better by x points” when the score decreases from baseline by x points, and as “Worse by x points” when the score increases by x points. For these scales, a Wilcoxon rank sum test will be used at each visit to obtain a p-value to compare the change status of each active treatment group to the placebo oral suspension.

For SGITS, PhGIC, and SGIC, the frequency of responses will be summarized for each scheduled collection timepoint. A stratified Wilcoxon rank sum test will be used at each visit to obtain a p-value to compare the results of each active treatment group to the placebo oral suspension.

The AIA-PRO consists of 13 questions each rated on a scale of 1 to 10 and mean total score. The mean total score is taken as the average of the 13 items. If any of the items is missing the mean total score will not be calculated. Descriptive statistics for actual and change from baseline for the mean total score and each individual item will be presented.

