### **3. INVESTIGATIONAL PLAN**

#### **3.1. Overall Study Design**

This Phase 2, multicenter, randomized, double-blind study is designed to evaluate the safety, tolerability and efficacy of ATI-501 Oral Suspension in subjects with AA, AU or AT. Subjects will be required to have a clinical diagnosis of stable AA, AU or AT with 30% to 100% total scalp hair loss for a duration of at least 6 months up to and including 12 years (inclusive). Stable AA, AU or AT is defined as no areas of spontaneous terminal scalp hair growth.

During the screening period, subjects will be assessed for eligibility into the study. Subjects will receive ATI-501 Oral Suspension, 400 mg, 600 mg, or 800 mg or Placebo Oral Suspension twice-daily for up to 24 weeks. Assessment of response to treatment will be performed at Week 4, Week 8, Week 12, Week 16, Week 20, Week 24, and post-treatment Week 28. Safety and tolerability will be evaluated at each study visit by assessment of adverse events, clinical laboratory tests, and vital signs, and at select visits, ECGs.

Subjects who complete study visits through Visit 9 will have the option to roll over into an open-label study ATI-502-AA-203. Subjects who withdraw consent or meet study medication discontinuation criteria (Section 3.4.1.2) on study ATI-501-AUAT-201 will not be eligible for roll-over to study ATI-502-AA-203. Subjects who complete the assessments for Visit 9 and then meet study ATI-502-AA-203 entry criteria and provide written consent will skip post-treatment Visit 10. Subjects who are not eligible for ATI-502-AA-203 or who decline to participate should return for the final Visit 10 assessments.

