**1.2. SCHEDULE OF ASSESSMENTS**

		Screening	Baseline	Treatment						Post-Treatment	
		Visit 1	Visit 2	Visit 3 	Visit 4	Visit 5	Visit 6	Visit 7	Visit 8	Visit 9 (ET)	Visit 10 
	Week		0	2	4	8	12	16	20	24	28
	Treatment Day	-30 to 0	1	15	29	57	85	113	141	169	197
	Treatment window (days)	N/A	N/A	±3	±3	±3	±3	±3	±3	±3	±3
	Informed consent 	X									
	Inclusion/exclusion criteria	X	X								
	Physical exam 	X								X	
	Demographics & medical history	X									
	Alopecia Areata History	X									
	Vital signs 	X	X	X	X	X	X	X	X	X	X
	Clinical Complete Blood Count (CBC), Chemistry, Virology, Serum Pregnancy, Urinalysis 	X 	X	X	X	X	X	X	X	X	X
	Blood for PK (Select Sites Only) 		X (Pre-dose)		X		X			X	
	Urine pregnancy test 	X	X		X	X	X	X	X	X	X
	ECG	X		X						X	
Subject 	Target Patch identification (Patchy AA Subjects Only)		X								
	Scalp-PRO Target Patch, Whole Scalp 		X	X			X			X	X
	Alopecia Facial Hair Appearance Assessment (AFHA: SR)		X	X			X			X	X
	Subject Global Impression of Severity (SGIS-AAP (patchy alopecia areata) or SGISAT/AU)		X	X			X			X	X
	Alopecia Impact Assessment (AIA): Subject Rating		X	X			X			X	X
	Subject Global Impression of Change (SGIC)									X	
	Subject Global Impression Treatment Satisfaction (SGITSAAP or SGITSAT/AU) 						X			X	X
	Subject Global Satisfaction with Hair Quality (SGSHQAAP or SGSHQAT/AU)		X	X			X			X	X
	DLQI 		X	X			X			X	X

		Screening	Baseline	Treatment						Post-Treatment	
		Visit 1	Visit 2	Visit 3 	Visit 4	Visit 5	Visit 6	Visit 7	Visit 8	Visit 9 (ET)	Visit 10 
Week			0	2	4	8	12	16	20	24	28
Treatment Day		-30 to 0	1	15	29	57	85	113	141	169	197
Treatment window (days)		N/A	N/A	±3	±3	±3	±3	±3	±3	±3	±3
Investigator 	Scalp-ClinRO Target Patch, Whole Scalp 		X	X			X			X	X
	Alopecia Facial Hair Appearance Assessment (AFHA: CR)		X	X			X			X	X
	Non-Scalp Hair Loss Assessment (NSHA)		X	X			X			X	X
	Physician Global Impression of Severity (PhGIS-AAP or PhGIS-AT/AU)		X	X			X			X	X
	Physician Global Impression of Change (PhGIC)									X	
	Hair Quality Assessment (Patchy AA Subjects Only)		X				X			X	X
	SALT Score (prior to ALODEX) 	X	X	X	X	X	X	X	X	X	X
	ALODEX Score (after SALT) 	X	X	X	X	X	X	X	X	X	X
Vellus and Indeterminate Hair Assessment	X	X	X	X	X	X	X	X	X	X	

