 Subjects who complete study visits through Visit 9 will have the option to roll over into an open-label study ATI-502-AA-203. Subjects who withdraw consent or meet study medication discontinuation criteria (Section 3.4.1.2) on study ATI-501-AUAT-201 will not be eligible for roll-over to study ATI-502-AA-203. Subjects who complete the assessments for Visit 9 and then meet study ATI-502-AA-203 entry criteria and provide written consent will skip post-treatment Visit 10. Subjects who are not eligible for ATI-502-AA-203 or who decline to participate should return for the final Visit 10 assessments.

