**Table 1: Visit Windows**

Nominal Visit	Target Study Day	Analysis Visit	Study Day Range
Screening	-30 to -1	Baseline	≤1
Day 1	1		
Week 2	15	Week 2	[12 – 22]
Week 4	29	Week 4	[23 – 42]
Week 8	57	Week 8	[43 – 70]
Week 12	85	Week 12	[71 – 98]
Week 16	113	Week 16	[99 – 126]
Week 20	141	Week 20	[127 – 154]
Week 24	169	Week 24	[155 – 182]

For the post-treatment visit 10, the analyses will be based on the nominal study visit as reported on the CRF.

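### The by-visit Wilcoxon tests in SAP 6.2.5 run on to Week 28, a visit that roll-over subjects skip by design, so the Week 28 p-values are not a valid randomised comparison of post-treatment status

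*SAP*

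**What the plan says.** SAP 6.2.5 covers Scalp-PRO, Scalp-ClinRO, PhGIS, AFHA, SGIS and the hair-quality scale in one sentence: "a Wilcoxon rank sum test will be used at each visit to obtain a p-value" for the change status of each active dose against placebo. For SGITS, PhGIC and SGIC the wording is "A stratified Wilcoxon rank sum test will be used at each visit to obtain a p-value". Neither sentence names a last visit. The primary MMRM in SAP 6.2.2, by contrast, is expressly limited to data up to Week 24.

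The schedule in SAP 1.2 (Protocol Table 3) marks Visit 10, Week 28, for Scalp-PRO, Scalp-ClinRO, AFHA, SGIS, PhGIS, SGSHQ and SGITS. PhGIC and SGIC are collected at Visit 9 only. The note under SAP Table 1 treats Visit 10 as an analysis visit: "For the post-treatment visit 10, the analyses will be based on the nominal study visit as reported on the CRF".

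Attendance at Visit 10 is governed by Protocol 3.1 and footnote 19 of the schedule. Subjects who complete the Visit 9 assessments, then meet the extension study's "entry criteria and provide written consent will skip post-treatment Visit 10". The rest are told to come: "Subjects who are not eligible for ATI-502-AA-203 or who decline to participate should return for the final Visit 10 assessments". Subjects who meet the discontinuation criteria of Protocol 3.4.1.2 cannot roll over.

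**The concern.** A between-arm p-value is normally read as a randomised comparison. At Week 28 that reading fails, because who is present is settled after 24 weeks of treatment by consent and by eligibility for another study. Both can depend on how the subject has fared.

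Week 28 is also the only off-treatment visit, so a p-value there invites a statement about whether the effect lasts or fades after stopping. What would be reported is that effect mixed either with who stayed behind or with carried-forward on-treatment scores, depending on how the SAP is programmed. The SAP gives no guidance on reading it.

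**Working it through.** **1. Do the tests reach Week 28?** Three provisions together say yes: a test at each visit (SAP 6.2.5), collection at Visit 10 (SAP 1.2) and an analysis rule for Visit 10 (note to SAP Table 1). Protocol 2.4 adds analyses at each applicable post-baseline visit with data, and Protocol 9.4.2 names Week 28 for SGITS, though only to be summarised. For the other scales Week 28 is inferred, not named.

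**2. Which data would enter?** The SAP can be read two ways.
- *Observed data.* SAP 6 uses non-missing denominators for by-visit percentages. In SAP 9 the tables for these scales carry no LOCF label, although the main SALT and ALODEX tables do.
- *LOCF.* SAP 4.3.4 carries the last value forward for missing clinical assessments with no exception for Visit 10, and SAP 5.1 uses the ITT population for all efficacy analyses.

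**3. The plan's own figures.** No stated figure concerns Week 28. The response rates used below, 32% (pooled 600 and 800 mg) and 6% (pooled placebo and 400 mg), come from SAP 4.1. They do reproduce the stated power: 95 × 0.90 / 2 = 42.75 per pooled group. At 42 to 43 per group, two-sided 0.05, power is 87.3% to 88.1% by normal approximation and 84.9% to 84.4% by exact enumeration with Fisher's test. This agrees with the stated values of more than 80% and no less than 84%.

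**4. Observed data: illustration.** Let p be the response rate, and let r_resp and r_non be the roll-over rates of responders and non-responders. The rate among attenders is

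p(1 − r_resp) / [p(1 − r_resp) + (1 − p)(1 − r_non)].

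Assume that nobody's status changes between Weeks 24 and 28 (true difference 32 − 6 = 26 points) and that the same rule holds in both arms. The 50% and 85% are assumptions.
- r_resp 0.50, r_non 0.85: 0.160/(0.160 + 0.102) = 61.1% v 0.030/(0.030 + 0.141) = 17.5%. Difference 43.5 points. Attenders out of 24: 24 × 0.262 = 6.3 and 24 × 0.171 = 4.1.
- r_resp 0.85, r_non 0.50: 0.048/(0.048 + 0.340) = 12.4% v 0.009/(0.009 + 0.470) = 1.9%. Difference 10.5 points. Attenders: 24 × 0.388 = 9.3 and 24 × 0.479 = 11.5.

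A common rule is therefore enough to distort the difference when Week 24 response differs between arms. SALT50 is analysed by logistic regression, not by the Wilcoxon test, and the two rates belong to pooled groups, so this shows the mechanism and does not forecast a result.

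**5. LOCF: illustration.** Assume an on-treatment effect of 0.8 SD that has gone by Week 28, and roll-over unrelated to response. The expected apparent Week 28 difference is roll-over share × 0.8 SD: 0.24, 0.40 and 0.56 SD at 30%, 50% and 70% roll-over. The true difference is zero.

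**6. Rejection rates.** These come from a simulated Wilcoxon test on a five-category scale with 24 per arm, 4,000 runs, nominal level 5% and no true Week 28 difference. With no roll-over the rate is 4.6%.

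| Assumed roll-over | 30% | 50% | 70% |
|---|---|---|---|
| Observed, unrelated to response | 4.9% | 4.6% | 3.4% |
| Observed, same selection in both arms, no drug effect at either visit | 4.5% | 4.5% | 2.5% |
| Observed, opposite selection by arm (extreme case) | 27% | 47% | 47% |
| LOCF, 0.8 SD effect fully faded | 11% | 24% | 40% |

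On observed data about 17, 12 and 7 of 24 per arm remain.

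**7. How many p-values?** Tables 14.2.4.1–4 (4), 14.2.5.1–4 (4), the AFHA tables (10) and 14.2.7.1–2 (2) make 20; 20 × 3 doses = 60. SGITS adds 2 tables × 3 = 6. The total is about 66.

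**The case against.** Four points on the other side have force.

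*The SAP does not name Week 28 in the Wilcoxon sentences, and the dated secondary endpoints in SAP 6.2.4 are at Week 24.* True, and the extension of the tests to Visit 10 is an inference for every scale except SGITS, for which the protocol itself names Week 28. But the schedule, the Visit 10 rule and the missing Week 24 limit all point the same way, and nothing in the SAP excludes Visit 10.

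*LOCF may keep the randomised arms whole.* A reader might infer flatly that the Week 28 p-values compare self-selected groups. The documents do not support that without a condition. If SAP 4.3.4 is applied literally, all randomised subjects with a value stay in, and the fault is a different one: on-treatment scores in an off-treatment comparison. Nor is the attending group only self-selected, since ineligible subjects are sent to Visit 10 too.

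*Selection on an observed result can be handled.* A reader might infer that no missing-at-random argument could help. That is not so. Every roll-over subject must have completed Visit 9, so if the choice depends on the Week 24 result, a model or weighting conditional on that result could address it. The planned Wilcoxon test does not condition on it.

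*Blinding limits the harm.* A reader might infer that the false-positive rate is inflated. The study is double-blind through Visit 9, and selection that works the same way in both arms, with no drug effect, leaves the rate at or below 5%. The rate rises on observed data only if selection differs by arm. That is conceivable, because response may differ and because the discontinuation criteria that bar roll-over include laboratory and infection events. The documents do not show it.

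**Conclusion.** The point holds as a defect in specification with limited scope. As written, the SAP calls for about 66 Week 28 p-values on secondary ordinal scales. Under either reading of the missing-data rules, none of them is a valid randomised comparison of post-treatment status. On observed data the comparison is confined to subjects who declined or were ineligible; under LOCF it mixes Week 24 on-treatment with Week 28 off-treatment scores.

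The size and direction of the distortion cannot be stated, because no roll-over rate is given. The range of about 44 to about 10 points around a true 26 rests on the assumed 50% and 85% rates, unchanged response status and a SALT50 endpoint. The rejection rates rest on the assumptions listed with them.

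It would be wrong to infer that the trial's main conclusions are at risk. The primary MMRM ends at Week 24, the SALT, ALODEX and DLQI change analyses follow its method, and the endpoints dated Week 24 are untouched. No objective concerns durability after stopping, and no decision rule uses Week 28.

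**What to change.** - In SAP 6.2.5, limit both Wilcoxon sentences (the plain and the stratified test) to each visit up to Week 24, and give no between-arm test at Visit 10.
- In SAP 4.3.4, state that LOCF is not used to fill a Visit 10 that was skipped because of roll-over. Without this, even a descriptive Week 28 table could be filled with Week 24 values.
- Present Visit 10 descriptively: numbers attending and rolled over per arm, Week 24 status of both groups, and the within-subject change from Week 24 to Week 28 among attenders, labelled as a non-randomised subset. The Week 28 summary of SGITS that Protocol 9.4.2 asks for is kept.

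Cost: a few words in the SAP, one small added table, and the loss of about 66 p-values on secondary scales. Sample size, power and data collection do not change.

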#### **6.2.6. Other Efficacy**

Results from the Hair Quality Assessment (hair pull test) will be summarized. The summary will show the shift relative to baseline in the categories of dislodged hairs and broken hairs at Week 24 (Visit 9).

Results from the Vellus and Indeterminate Hair Assessment will be summarized. The summary will show the shift relative to baseline at Week 24 (Visit 9) in the categories of vellus hair present and indeterminate hair present.

NSHA results will also be summarized. The summary will show the shift relative to baseline at Week 24 (Visit 9) in the Body Hair Loss categories of no body hair loss, some hair loss, and total body hair loss and in the Nasal Hair Loss categories of no nasal hair loss to some to total hair loss.

#### **6.2.7. Subset Analyses**

- Subgroups of Baseline SALT score group ( $< 50$ ,  $\geq 50$ )
- Subgroups of duration of current alopecia episode ( $< 4$  years,  $\geq 4$  years)

The primary analysis of the percent change in SALT score over time, the analysis of percent change in ALODEX score over time, and all planned responder-type analyses will be repeated in each subgroup.

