#### **4.3.2. Examination of Subject Subsets**

The baseline SALT score group ( $< 50$ ,  $\geq 50$ ) will be used for subset analyses. Additionally, duration of current episode ( $< 4$  years,  $\geq 4$  years) will be used for subset analyses. The details of the subset analyses are given in the statistical analysis section.

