#### **4.3.3. Multiple Testing and Comparisons**

There are no planned adjustments for multiple comparisons.

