## **6. STATISTICAL METHODS**

Descriptive statistical methods will also be used to summarize the data from this study, with hypothesis testing performed for the primary and key secondary efficacy endpoints. Unless stated otherwise, the term “descriptive statistics” refers to number of subjects, mean, median, standard deviation, minimum, and maximum for continuous data, and frequencies and percentages for categorical data. For categorical variables, the denominator of percentages will be the number of subjects in the treatment group, except for those collected by study visit and/or scheduled time point, in which case the denominator of percentages will be the number of subjects with a non-missing value at the visit and/or the scheduled time point. If a different denominator is used, this will be identified in the summary table.

All data collected during the study will be included in data listings. Unless otherwise noted, the data will be sorted first by treatment group, subject number, and then by date within each subject number.

The term ‘treatment group’ refers to ATI-501 active groups and matching Placebo Oral Suspension group.

All statistical testing will be two-sided and will be performed using a significance (alpha) level of 0.05 unless otherwise stated. P-values will be presented to three decimal places. For the efficacy

endpoints, the ATI-501 treatment groups will be tested versus Placebo Oral Suspension via statistical inference.

The statistical analyses will be conducted with the SAS® software package version 9.4 or higher. All analyses will be subject to formal verification procedures. Specifically, results will be independently verified by a second programmer/statistician prior to issuance of the draft statistical report. All documents will be reviewed by the lead statistician to ensure accuracy and consistency.

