### Other Efficacy

52. Table 14.2.9.1 Subject Global Impression of Treatment Satisfaction (SGITS) over Time, AAP Subjects, ITT Population
53. Table 14.2.9.2 Subject Global Impression of Treatment Satisfaction (SGITS) over Time, AU/AT Subjects, ITT Population

- 54. Table 14.2.10.1 Summary of DLQI Score and Change from Baseline by Visit, ITT Population
- 55. Table 14.2.10.2 Analysis of Change from Baseline in DLQI Total Score over Time, ITT Population
- 56. Table 14.2.11.1 AIA-PRO, Total Score, ITT Population
- 57. Table 14.2.11.2 AIA-PRO, Cover Hair Loss, ITT population
- 58. Table 14.2.11.3 AIA-PRO, Worried about Appearance, ITT population
- 59. Table 14.2.11.4 AIA-PRO, Sad Due to Hair Loss, ITT population
- 60. Table 14.2.11.5 AIA-PRO, Confidence, ITT population
- 61. Table 14.2.11.6 AIA-PRO, Self-Conscious, ITT population
- 62. Table 14.2.11.7 AIA-PRO, Embarrassed, ITT population
- 63. Table 14.2.11.8 AIA-PRO, Unattractive, ITT population
- 64. Table 14.2.11.9 AIA-PRO, Limit Social Activity, ITT population
- 65. Table 14.2.11.10 AIA-PRO, Limit Physical Activity, ITT population
- 66. Table 14.2.11.11 AIA-PRO, Unwanted Attention, ITT population
- 67. Table 14.2.11.12 AIA-PRO, Sweat in Eyes, ITT population
- 68. Table 14.2.11.13 AIA-PRO, Debris in Eyes, ITT population
- 69. Table 14.2.11.14 AIA-PRO, Debris in Nose, ITT population
- 70. Table 14.2.12 Shift from Baseline to Week 24 in Hair Pull Test Results - Dislodged Hairs and Broken Hairs, AAP Subjects, ITT Population
- 71. Table 14.2.13 Shift from Baseline to Week 24 in Vellus and Indeterminate Hair Assessment Results, ITT population
- 72. Table 14.2.14, Shift from Baseline to Week 24 in Non-Scalp Hair Loss (NSHA) Assessment Results – Body Hair Loss and Nasal Hair Loss, ITT population

Subgroup Analyses

- 73. Table 14.2.15.1 Analysis of Percent Change from Baseline in SALT Score (LOCF), ITT Population, Baseline SALT < 50
- 74. Table 14.2.15.2 Analysis of Percent Change from Baseline in SALT Score (LOCF), ITT Population, Baseline SALT  $\geq$  50
- 75. Table 14.2.15.3 Analysis of Percent Change from Baseline in SALT Score (LOCF), ITT Population, Duration of Current Alopecia Episode < 4 Years
- 76. Table 14.2.15.4 Analysis of Percent Change from Baseline in SALT Score (LOCF), ITT Population, Duration of Current Alopecia Episode  $\geq$  4 Years
- 77. Table 14.2.16.1 Analysis of Percent Change from Baseline in ALODEX Score (LOCF), ITT Population, Baseline SALT < 50

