- 108. Table 14.2.23.4 Proportion of Subjects with  $\geq 1$  Point Improvement in Scalp-PRO for Entire Scalp, ITT Population, Duration of Current Alopecia Episode  $\geq 4$  Years

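### The SAP repeats nine analyses separately in four subgroups but plans no estimate of how the treatment effect differs between subgroups, and it drops the one interaction term the protocol had

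*SAP*

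**What the plan says.** SAP 4.3.2 names baseline SALT group as a factor that "will be used for subset analyses" and adds a second: "Additionally, duration of current episode", cut at 4 years. It defers the details to the statistical methods. SAP 6.2.7 then says only that the percent-change analyses of SALT and ALODEX and "all planned responder-type analyses will be repeated in each subgroup".

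The table list in SAP section 9 carries this out, from item 73, "Table 14.2.15.1 Analysis of Percent Change from Baseline in SALT Score (LOCF), ITT Population, Baseline SALT < 50", to item "108. Table 14.2.23.4 Proportion of Subjects with" a one-point or greater Scalp-PRO improvement in episodes of 4 years or more.

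The repeated models have no subgroup term. The MMRM in SAP 6.2.2 has treatment, visit and their interaction. The logistic model in SAP 6.2.5 has treatment alone. SAP section 6 sets the testing rule: "All statistical testing will be two-sided and will be performed using a significance (alpha) level of 0.05 unless otherwise stated", and for efficacy "the ATI-501 treatment groups will be tested versus Placebo Oral Suspension via statistical inference". SAP 4.3.3 states: "There are no planned adjustments for multiple comparisons".

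The protocol differs. Its primary model (Synopsis and 9.4.1) includes baseline SALT group and a treatment by SALT group interaction. SAP 6.2.2 has neither, while SAP section 7 reports no departure from the protocol's analyses.

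**The concern.** A subgroup question asks whether the effect differs between two groups of subjects. Two separate fits, each tested against zero, do not answer it. When power within each subgroup is moderate, one will often cross 0.05 and the other will not, even if the drug works equally well in both. Without a planned contrast, the printed results invite exactly that comparison, across 36 tables and three doses.

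For baseline SALT there is also a conflict between the documents. The protocol's model holds a term that could have supplied the comparison, and the SAP removes it without saying so. For episode duration neither document plans any comparison.

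**Working it through.** **1. Count of tables.** There are two percent-change analyses and seven responder endpoints (SAP 6.2.5, counting SALT and ALODEX ≥50% regrowth separately), so 9 × 4 subgroups = 36. The list agrees: 108 − 73 + 1 = 36. Items 73 to 80 are the 8 percent-change tables and items 81 to 108 the 28 responder tables.

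**2. The plan's own power figure.** SAP 4.1 assumes SALT50 rates of 32% (600 + 800 mg) and 6% (placebo + 400 mg), N = 95 and 10% dropout. Per pooled group this leaves 95 × 0.9 / 2 ≈ 43 subjects. Power at 42 to 43 per group, two-sided 0.05:
- normal approximation: 0.87 to 0.88
- with continuity correction: 0.80 to 0.81
- Fisher exact: 0.84 to 0.85

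So the stated figure of more than 80% reproduces, and the 84% quoted for the primary analysis matches the Fisher value. Both come from a pooled comparison, whereas the subset tests compare each dose with placebo.

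**3. Chance that exactly one subgroup is significant under a uniform effect.** If overall power is P, the noncentrality is t = 1.96 + z(P). A subgroup holding a share f of subjects has power Φ(t√f − 1.96). Call the two powers a and b. The subgroups share no subjects, so the chance is a(1 − b) + b(1 − a).

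The documents give no subgroup split, so f is assumed. About 45 of 95 subjects have AT or AU, which protocol Table 5 defines as more than 95% loss, so all of them fall in SALT ≥50. If the other 50 were spread evenly over 30 to 95, then 50 × 20/65 ≈ 15.4 would have SALT <50, or about 4 per arm.

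| Overall power | Even split | 25 of 95 | 15.4 of 95 |
|---|---|---|---|
| 80% (t = 2.80) | 0.50 | 0.57 | 0.64 |
| 84% (t = 2.95) | 0.50 | 0.58 | 0.65 |
| 90% (t = 3.24) | 0.47 | 0.57 | 0.67 |

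Worked case at 80%, 15.4 of 95: a = 0.203, b = 0.727, and 0.203 × 0.273 + 0.727 × 0.797 = 0.635.

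**4. One dose on SALT50.** At about 24 per arm and 32% versus 6%, full-arm power is 0.64 (normal approximation) or 0.57 (Fisher). Simulated binomial data with per-arm splits of 12/12, 10/14 and 5/19 give an exactly-one rate of 0.44 to 0.55 by chi-square and 0.30 to 0.43 by Fisher. If the reader looks at either of the 600 and 800 mg doses, the rate is 0.67 to 0.75 by chi-square or 0.48 to 0.61 by Fisher.

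**5. Direct contrast.** In the same uniform-effect setting, simulated at 55, 80 and 84% power, testing the difference between subgroup effects gives a false difference in 4.9 to 5.0% of trials.

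**6. Precision of the contrast.** Its standard error is that of the overall effect divided by √(f(1 − f)). For an interaction as large as the overall effect, at t = 2.80, power is Φ(2.80 × 0.5 − 1.96) = 0.29 for an even split. With 15.4 of 95, √(0.162 × 0.838) = 0.368 and power is Φ(2.80 × 0.368 − 1.96) = 0.18.

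**The case against.** The strongest reply is that the planned output already allows the comparison. SAP 6.2.2 gives treatment differences with 95% CIs and SAP 6.2.5 gives odds ratios with 95% CIs. The subgroups are disjoint and separately fitted, so a reader could derive the contrast and its interval. SAP 6.2.2 does not itself name a p-value; that comes from the general rule in section 6. This stands: the information is recoverable. What is missing is the plan to report it and to judge subgroups by it.

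A reader might infer that a uniform effect will look subgroup-specific at least half the time in this trial. The documents do not support that as a general statement. They derive 80% power only for pooled groups and then assert at least as much for the primary analysis. At the power of one dose on SALT50 the rate can be 30%. At 95% power with an even split it is 40%.

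A reader might also infer that one joint model would sharpen the subset intervals by pooling variance. That does not apply to the 28 logistic tables, which estimate no residual variance. It is doubtful for percent change too: a 10-point SALT change is 25% at a baseline of 40 but 10% at a baseline of 100, so equal variance across SALT groups cannot be presumed.

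Nor do the documents say that subset results will choose the next trial's population. The amendment history describes an exploratory initial Phase 2 study. Omitting within-subgroup p-values is a reporting preference and not a correction.

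**Conclusion.** The point holds as a gap in the subset analyses and a protocol–SAP discrepancy. It does not touch the overall dose-versus-placebo estimate. The SAP plans 36 separate subgroup tables and no estimate of effect difference for either factor, and it omits the protocol's SALT-group interaction while claiming consistency. The protocol describes no test or report of that term. It is also not crossed with visit, so as written it would describe a difference averaged over visits and not one at Week 24.

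Given a uniform effect and 80 to 84% power for a dose-versus-placebo comparison, one-subgroup-only significance occurs about 50% of the time with an even split and about 64% with roughly 15 of 95 in SALT <50. For one dose on SALT50 it is about 30 to 55%. These figures rest on the assumed split, the assumed per-dose power and, for percent change, a known-variance approximation that is rough at about 4 subjects per arm.

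**What to change.** In SAP 6.2.7, for each factor, add the Week 24 difference between subgroup treatment effects for each dose versus placebo, with a 95% CI:

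- **Percent change in SALT and ALODEX:** take it from one model per factor with treatment × visit × subgroup (and lower-order terms), letting the variance differ by subgroup.
- **Responders:** report the difference between subgroup risk differences with a 95% CI, or counts only where cells are too small.
- **Protocol–SAP conflict:** reconcile the dropped treatment by SALT group interaction, either by restoring it or by recording and justifying the change in SAP section 7.
- **Interpretation:** label the subsets exploratory, and state that a subgroup difference will be judged on this contrast and not on significance in one subgroup versus the other.

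The cost is SAP wording and a modest amount of programming; no new data are needed. The limitation should be written in as well. With about 18 to 29% power for an interaction as large as the overall effect, the interval will be wide, and a non-significant contrast does not show that the effect is uniform.
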